## ABBREVIATIONS AND DEFINITIONS

AE	adverse event	LDAC	low-dose Ara-C
AML	acute myelogenous leukemia	MDS	myelodysplastic syndromes
ANC	absolute neutrophil count	MedDRA	Medical Dictionary for Regulatory Activities
BDM	Biostatistics and Data Management	NCCN	National Comprehensive Cancer Network
BID	twice daily	NDAOH	number of days alive and out of the hospital
BM	bone marrow	NE	nonevaluable
BSA	body surface area	NR	nonresponders
CI	confidence interval	OR	odds ratio
C max	maximum concentration	OS	overall survival
CR	complete response	PB	peripheral blood
CRc	composite CR (CRc = CR + CRp + CRi)	PD	pharmacodynamic(s)
CRi	CR with incomplete blood count recovery	PFS	progression-free survival
CRO	contract research organization (CRO)	PK	pharmacokinetic(s)
CRp	CR with incomplete platelet recovery	PR	partial response
CTCAE	Common Terminology Criteria for Adverse Events	PT	preferred term
DMC	Data Monitoring Committee	QOL	quality of life
ECG	electrocardiogram	QTc	heart rate corrected QT interval
ECOG	Eastern Cooperative Oncology Group	ROW	rest of world
EQ VAS	EQ visual analogue scale	Remission	equivalent to "response"
FAB	French-American-British	Response	equivalent to "remission"
HCT	hematopoietic cell transplant	RR	relative risk
HR	hazard ratio	SAE	serious adverse event
ITT	intent-to-treat	SAP	statistical analysis plan
IWG	International Working Group	SC	subcutaneous
		SGI-110	guadecitabine
		SOC	system organ class
		TC	treatment choice

## 1.0 INTRODUCTION

This Statistical Analysis Plan (SAP) is based on SGI-110-04 protocol version 2, dated 6 March 2015. Analyses and statistical reporting for SGI-110-04 will be conducted by Astex Pharmaceuticals Biostatistics department with the interim analysis results as reported by the study's Data Monitoring Committee (DMC).

### 1.1 Acute Myeloid Leukemia in Patients Who Are Not Considered Candidates for Intensive Remission Induction Therapy and the Elderly

Acute myeloid leukemia (AML) is a genetically heterogeneous group of cancers that have in common clonal proliferation and arrested differentiation of myeloid precursors. Incidence increases with age and is about 12 cases per 100,000 for those at and above the median age at diagnosis of 65 years ([Schiffer and Anastasi 2014](#)). Overall 5-year survival is 15% and varies substantially with age ([Shah et al 2013](#)). Patients age 70-79 years and over age 79 years have 5 year survival rates of 3% and 0%, respectively.

In addition to age, other adverse prognostic indicators in AML include poor performance status, adverse cytogenetic or molecular genetic findings, past exposure to cytotoxic or radiation therapy, and history of myelodysplasia or another hematologic disorder ([Schiffer 2014](#)). There is a correlation between age at diagnosis of AML and complex cytogenetic disease characteristics. Complex karyotype also correlates with disease resistance to therapy ([Grimwade et al 2001](#)). In summary, AML in patients who are not considered candidates for intensive remission induction chemotherapy, particularly elderly patients, remains a persistent unmet medical need.

### 1.2 Treatment Options for Patients with AML Who Are Not Considered Candidates for Intensive Remission Induction Therapy

No standard therapy exists for patients with previously untreated AML who are not candidates for intensive remission induction chemotherapy. The National Comprehensive Cancer Network (NCCN), European Leukemia Net, and European Society for Medical Oncology all recommend possible treatments with low-dose Ara-C (LDAC), azacitidine, or decitabine in addition to enrolling patients in experimental treatment clinical trials.

In Study SGI-110-04, treatment choice (TC) will be compared with guadecitabine (SGI-110). Available TCs will depend on which TCs are approved locally. TC includes cytarabine, decitabine, or azacitidine.

### 1.3 Guadecitabine

Guadecitabine is a dinucleotide of decitabine and deoxyguanosine, designed to protect the active decitabine moiety from inactivation by cytidine deaminase ([Griffiths et al 2013](#)).

Rationale for Study SGI-110-04 comes from guadecitabine's molecular structure, pharmacokinetic (PK), pharmacodynamic (PD), and clinical data. Human PK data confirms that

gradual in vivo dinucleotide cleavage increases decitabine exposure time and effective half-life relative to decitabine IV infusion. Prolonged exposure time is predicted to increase efficacy because decitabine activity is dependent on its incorporation into DNA during DNA synthesis, ie, S-phase of the cell cycle (Griffiths et al 2013; Karahoca and Momparler 2013). Prolonged exposure results in more cancer cells susceptible to decitabine activity as they enter into S-phase. Also, a lower decitabine  $C_{max}$  after guadecitabine relative to decitabine IV infusion might improve safety for toxicities associated with peak decitabine concentrations.

During the first-in-human Phase 1 SGI-110-01 Dose Escalation, potent DNA demethylation, complete response (CR) and other clinical responses were observed in heavily pretreated subjects with AML and MDS (myelodysplastic syndromes) (Issa et al 2015), including those previously treated with other existing hypomethylating agents (decitabine and azacitidine).

In the Phase 2 SGI-110-01 Dose Expansion, 51 elderly subjects with AML who had other poor prognostic features and were not eligible for intensive chemotherapy received guadecitabine. The CR rate of 37% and composite CR (CRc) rate of 57% (Kantarjian et al 2015) exceeded those observed for available therapies in randomized, multicenter studies (CR rates of 8% to 20% and CRc rates of 11% to 28%) (Kantarjian et al 2012; Dombret et al 2014; Burnett et al 2007).

## 2.0 STUDY OBJECTIVES

### 2.1 Primary Objective

To assess and compare efficacy (CR rate and overall survival [OS]) between guadecitabine and TC in adults with previously untreated AML who are not considered candidates for intensive remission induction chemotherapy.

### 2.2 Secondary Objectives

To assess and compare effects of guadecitabine and TC in adults with previously untreated AML who are not considered candidates for intensive remission induction chemotherapy with respect to the following variables:

- CRc (CR + CR with incomplete blood count recovery [Cri] + CR with incomplete platelet recovery [CRp]) rate.
- Number of days alive and out of the hospital (NDAOH).
- Progression-free survival (PFS).
- Transfusion needs.
- Health-related quality of life (QOL).
- Duration of CR.
- Safety.

## 2.3 Exploratory Objectives

- [REDACTED]
- [REDACTED]

## 3.0 STUDY DESIGN

### 3.1 Overall Study Design

This is a phase 3, multicenter, randomized, open-label study of guadecitabine versus TC. Blinded central reading of marrow and disease response will be performed. Subjects will be adults with previously untreated AML who are unfit to receive and not candidates for intensive remission induction chemotherapy.

Approximately 800 subjects from approximately 100-160 study centers will be randomly assigned (1:1) to 1 of 2 groups:

- Guadecitabine: 60 mg/m^2 guadecitabine given SC daily for 5 days (Days 1-5, Daily×5) in 28-day cycles.
- TC: subjects will be assigned (before randomization) by the investigator to 1 of the following treatment regimens:
  - 20 mg cytarabine (Ara-C) given SC BID on Days 1-10 every 28 days.
  - 20 mg/m^2 decitabine (Dacogen) given IV on Days 1-5 every 28 days.
  - 75 mg/m^2 azacitidine (Vidaza) given IV or SC on Days 1-7 every 28 days.

The randomization will have a ratio of 1:1 between guadecitabine and TC groups, and will be stratified by age (<75 or ≥75 years old), ECOG performance status (0-1, 2-3), study center region (North America, Europe, rest of world [ROW]), and secondary AML or poor-risk cytogenetics (Yes, No/Unknown). Subjects who are older (≥75 years) or have a poor performance status (2 or 3) tend to have worse response and survival than younger (<75 years) subjects or subjects with a good performance status (0 or 1). Similarly, subjects with a secondary AML or poor-risk cytogenetics generally do not respond to treatment well and have a shorter survival time. In addition, prognosis could have regional differences due to multiple factors including variable levels of Standard of Care. Stratification by these known and important prognostic factors measured at baseline prevents imbalance between treatment groups within strata, and could reduce bias and improve power of the study.

Selection of 1 of the TCs must be made prior to the randomization of each subject. Subjects should receive study treatment as soon as possible after randomization (maximum of 1 week between randomization and treatment).

The sponsor, investigators and study subjects are not blinded in this study. However, to minimize the potential bias associated with assessment of treatment outcome, response will be determined

[figure not shown]

by a blinded independent central response reviewer, based on assessment by a blinded independent central pathologist. Refer to Section 11.6 of the study protocol. The specific process used for handling test samples and reports will be described separately.

Peripheral blood (PB) will be assessed at baseline and on Day 1 of each cycle for response status evaluation. Bone marrow (BM) aspirate/biopsy will be performed at screening and then at the end of Cycles 2, 4, and 6 unless PB shows persistence of leukemic blasts that excludes the possibility of a marrow response. After Cycle 6 BM assessment, BM aspirate/biopsy will be repeated every 3 months for the first year on study and then every 6 months thereafter until PB or BM assessment shows disease progression or relapse. Response evaluation will be based on BM blinded assessment and the most concomitant PB counts. After blinded BM response is confirmed, assessment of normal count recovery will be done based initially on the most concomitant PB and in later cycles on PB counts from Day 1 of each cycle to avoid transient treatment-induced normal count suppression.

Figure 1 below summarizes the study design.

**Figure 1: Study Schema**

a Treatment with guadecitabine should continue for at least 6 cycles in the absence of unacceptable toxicity or AML progression requiring alternative therapy. Beyond 6 cycles, treatment should continue as long as the subject continues to benefit based on investigator judgment.

b TC will be determined before randomization and treatment with the regimens described in the study protocol (Section 7.2) should be used. Other treatment parameters should be applied according to institutional standard practice and approved local prescribing information.

The study is expected to enroll the required number of subjects in 21 months with an additional follow-up of 12-15 months before the planned primary analysis. The expected duration of the study from the first subject enrollment to the planned primary analysis is approximately 3 years.

## 3.2 Study Endpoints

### 3.2.1 Co-primary Endpoint

- CR rate based on modified International Working Group (IWG) 2003 AML Response Criteria.
- OS, defined as the number of days from randomization to death.

### 3.2.2 Secondary Endpoints

- CRc (CR+CRi+CRp) rate.
- NDAOH.
- PFS, defined as the number of days from date of randomization to date of disease progression, initiation of an alternative anti-leukemia therapy, or death, whichever occurs first.
- Number of red blood cell (RBC) or platelet transfusions (units) over the duration of the study treatment.
- Health-related QOL by EQ-5D (consisting of the EQ-5D-5L descriptive system and the EQ Visual Analogue Scale [EQ VAS]).
- Duration of CR, defined as the time from first CR to time of relapse.
- Incidence and severity of adverse events (AEs).
- 30- and 60-day all-cause mortality.

## 4.0 SAMPLE SIZE

By trial design, the overall (2-sided) alpha level of 0.05 is split between the co-primary endpoints of CR (0.04) and OS (0.01). A formal interim analysis will be performed only for OS using a group sequential boundary preserving an overall (2-sided) 0.01 alpha level. The sample size calculation for the primary analysis of CR is based on testing at the 0.04 nominal alpha level. If statistical significance is achieved for CR, hierarchically, the final analysis of OS will be conducted to preserve an overall 2-sided 0.05 alpha level, accounting for alpha spent at the interim analysis of OS, as described in Section 11.6.7 and Section 11.9 of the study protocol (see Section 7.3.7 and 7.6). The sample size calculation for OS will be shown for the setting of a 2-sided 0.05 alpha level.

Assuming a CR rate of approximately 0.20 ([Kantarjian et al 2012](#); [Fenaux et al 2010](#); [Burnett et al 2007](#)) for subjects treated in the TC group (all TC therapies combined) and assuming an increase in CR rate to 0.30 or higher can be achieved by treating subjects with guadecitabine,

800 subjects (400 per treatment group) will provide approximately 89% power to detect the overall difference of 0.10 when using a 2-sided Cochran Mantel-Haenszel test having 2-sided alpha level of 0.04. For the purpose of this sample size calculation, the constant CR rates of 0.20 and 0.30 for the TC and guadecitabine groups, respectively, are assumed for each stratum.

For survival, an analysis at 670 death events will provide 90% power to detect a HR of approximately 0.78 (a difference in median survival of 7 months in the TC group versus 9 months in the guadecitabine group), when using a 2-sided stratified log-rank test at an 0.05 alpha level. Accrual is expected to be uniform over a 21 month enrollment period, with an additional follow-up of 12 months. Hence, the assessment of survival needs approximately the same sample size of 800 subjects. Primary response and survival analyses will be performed after 670 death events have occurred. For the purpose of this sample size calculation, a constant HR of approximately 0.78 was assumed for all strata defined by the stratification factors.

## **5.0 ANALYSIS SETS**

### **5.1 All Subject Analysis Set**

This analysis set will contain information of all screened subjects, including those who did not meet the study entry criteria or did not receive a study treatment.

### **5.2 Efficacy Analysis Set**

Efficacy analyses will be based on intent-to-treat (ITT) principle. The Efficacy Analysis Set will include data from all subjects randomly assigned to study treatment. All data will be included and no subjects excluded because of protocol violations. For the analysis of efficacy data, subjects will be included in the treatment group according to their randomly assigned treatment.

For NDAOH, transfusions, and health-related QOL by EQ-5D-5L, the primary analysis will include only the data collected during the first 6 months of the study because, during this study period, subjects are assessed whether or not they are still on study treatment. Secondary analysis may also include data beyond the first 6 months of the study (eg, over the entire period of study treatment).

### **5.3 Safety Analysis Set**

The Safety Analysis Set will include data from all subjects randomly assigned to study treatment who receive any amount of study treatment or any component of a multi-dose study treatment regimen. All data will be included and no subjects excluded because of protocol violations. For safety data analysis, subjects will be included in the treatment group according to the treatment they actually receive. If more than one type of study treatment was given for any subject during the study, the initial treatment received by the subject will be used to determine which treatment group and which specific TC treatment the subject belongs to.

## 5.4 PK Analysis Set

The PK Analysis Set will include all available plasma concentrations and PK parameters for guadecitabine and decitabine from subjects at selected centers who have received guadecitabine or decitabine IV and for whom PK samples were collected and successfully analyzed. PK data will be analyzed using the PK Analysis Set.

## 5.5 PD Analysis Set

Pharmacodynamics analyses are not applicable to this study.

## 6.0 SCHEDULE OF ANALYSES

Data listings and summary tables will be reviewed by the DMC approximately every 6 months to ensure the safety of study subjects and to enhance the quality of trial conduct (refer to protocol Section 4.4 and the DMC Charter). These data listings and summary tables will be generated by Axio Research LLC, an independent contract research organization (CRO) supporting the DMC activities.

An interim analysis of OS will also be conducted by the DMC when approximately half of the required death events have occurred. All available study data will be analyzed after 670 death events have occurred to achieve a mature analysis of OS.

## 7.0 STATISTICAL ANALYSIS

Unless otherwise specified, all statistical tests and confidence intervals (CIs) created will be two-sided with  $\alpha = 0.05$  (see Section 7.3.7). The SAS® statistical package (SAS Institute Inc., Cary, NC, USA, version 9.3 or a later version) will be used for the analyses.

The following data listings by study center and subject will be provided, as recommended by the ICH E3 guideline "Structure and Content of Clinical Study Reports": discontinued subjects, important protocol deviations, demographics, compliance and/or drug concentration data (including specific batch number), individual efficacy response data, subjects excluded from the efficacy analysis, AEs, medications, and the protocol specified laboratory measurements. Additional data listings may be generated to support other relevant discussions in CSR.

Summary tables of disposition, baseline, dosing, efficacy, safety, and PK data will be provided, by treatment group (guadecitabine or TC). In addition, similar tables will be generated, as appropriate, comparing guadecitabine to each TC option in the patients randomized under that preselected TC option.

### 7.1 Subject Disposition

Subject disposition including numbers screened, randomized, treated, and treatment discontinuation by reason, as well as the reasons for withdrawal from study will be summarized using frequencies and percentages based on information collected on the relevant study case

report form pages. Sample size for efficacy and safety analysis sets will be clearly identified. All Subject Analysis Set will be used for the disposition analysis.

## 7.2 Demographic and Other Baseline Characteristics

The demographic variables consist of age, age category, sex, ethnicity, race and geographical region. Baseline characteristics include height, weight, body surface area (BSA), ECOG performance status, AML category by French-American-British (FAB) classification as well as by WHO classification, time since AML diagnosis, whether the AML is secondary to MDS or other antecedent hematologic disorder, cytogenetic risk levels, peripheral blood counts of hemoglobin, platelets, total white blood cells (WBCs) with blasts counts, BM blasts and presence of baseline genetic mutations in several genes including but not limited to FLT3-ITD, NPM1, and CEBPA. Other baseline variables such as relevant medical history or other medically relevant criteria could also be included in the baseline tables.

Baseline values are generally the values collected right before randomization during the screening period. For analysis purposes, the value collected closest to but before randomization will be used as the baseline value for a particular variable. For variables which are collected on Day 1 of Cycle 1 (C1D1) but not during the screening period, the C1D1 values will be used as the baseline values.

Age at baseline, if not already provided through data collection, will be calculated as the integer part of  $(\text{date of consent} - \text{date of birth})/365.25$ .

Time since diagnosis will be calculated as the  $(\text{date of randomization} - \text{date of diagnosis})$ . If the day is missing for date of diagnosis, the 15th of the month is used. If the month is missing, July 1st is used. If the year is missing, the date is left as missing. Additional date imputation details are contained in the Astex Data Programming Conventions.

Subject demographic and baseline characteristics will be summarized by mean, standard deviation, median, minimum, and maximum for continuous variables; and by counts and percentages for categorical variables. Both the Efficacy and Safety Analysis Sets will be used for the summaries.

## 7.3 Efficacy Variables and Analyses

Efficacy analyses will be based on the Efficacy Analysis Set, except where it is specified otherwise. This section describes the analyses conducted at the primary analysis time point when 670 death events have occurred, assuming that the study continued after the planned interim analysis. The alpha levels referenced in this section are nominal alpha levels for judging statistical significance, taking into consideration the planned interim analysis and the hierarchical testing order of the (final) primary analysis. The overall experimental alpha error is controlled at the 2-sided 0.05 level.

The co-primary efficacy endpoints are CR rate based on IWG 2003 AML Response Criteria ([Cheson et al 2003](#)) and OS. If either of the co-primary efficacy endpoints reaches statistical

significance in favor of guadecitabine at either the interim analysis (OS only) or final analysis (CR and OS), then the study will be considered positive in efficacy.

Secondary efficacy endpoints include CRc, NDAOH, PFS, number of RBC transfusions, and separately, number of platelet transfusions over the duration of the study treatment, the EQ-5D-5L descriptive system and the EQ VAS, as well as duration of CR.

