4.2 Discussion of Study Design

This trial compares SGI-110 and TC for treatment of subjects with AML who are not considered candidates for intensive remission induction chemotherapy at the time of enrollment. While the 7+3 intensive chemotherapy for remission induction with potential for hematopoietic cell transplant (HCT) has been an established standard of care for decades in patients who are fit to receive this intensive treatment, there is no standard of care or universally approved therapies for treatment of AML patients who are not candidates for standard intensive remission induction chemotherapy. For these patients, goals of therapy are to prolong and improve quality of life by inducing complete remission for as long as possible, as well as to avoid treatment-induced early mortality.

Eligibility for this trial is based on precedented criteria of unsuitability for intensive remission induction chemotherapy (Ferrara et al 2013; Kantarjian et al 2006; Kantarjian et al 2010) and other randomized trials in a similar patient population (Burnett et al 2007; Kantarjian, Thomas et al 2012; Dombret et al 2014). The co-primary endpoints for this trial are CR rate and OS.

FDA has accepted durable CR in hematological malignancies as an established surrogate for clinical benefit because patients who achieve durable CR have been shown to survive longer than those who do not (Appelbaum et al 2007). Numerous studies have demonstrated that subjects achieving CR survive longer than subjects not achieving CR (Sievers et al 2001; Larson et al 2005; de Greef et al 2005; Kantarjian et al 2003). FDA has also granted regular approval for treatment of hematologic malignancies on the basis of durable CR. In these settings, durable CRs were considered an established surrogate for a better life and possibly a longer life (Johnson et al 2003).

The trial includes a co-primary endpoint of OS to confirm no decrement in survival from severe toxicity. Secondary endpoints include CRc (CR+CRi+CRp) rate, NDAOH, PFS, number of transfusions, health-related QOL, duration of CR, and safety.

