11.6 Efficacy Analyses

Efficacy analyses will be based on the Efficacy dataset. Unless otherwise specified, this section describes the analyses conducted at the primary analysis time point when 670 death events have occurred, assuming that the study continued after the planned interim analysis. The alpha levels referenced in this section are nominal alpha levels for judging statistical significance, taking into consideration the planned interim analysis and the hierarchical testing order of the (final) primary analysis. The overall experimental alpha error is controlled at the 2-sided 0.05 level.

The co-primary efficacy endpoints are

- CR rate by modified IWG 2003 AML Response Criteria ([Cheson et al 2003](#)) as described in Section 11.6.1. Assessments will be blinded as described in Section 11.6.1.
- OS, defined as the number of days from randomization to death.

If either of the co-primary efficacy endpoints reaches statistical significance in favor of SGI-110 at either the interim analysis (OS only) or final analysis (CR and OS), then the study will be considered positive in efficacy.

Secondary efficacy endpoints are the following and will be defined in more detail in the statistical analysis plan:

- CRc (CR+CRi+CRp) rate.
- NDAOH.
- PFS, defined as the number of days from randomization to disease progression or death, whichever occurs first.
- Number of RBC or platelet transfusions (units) over the duration of the study treatment.
- Health-related QOL by EQ-5D-5L (consisting of the EQ-5D-5L descriptive system and the EQ Visual Analogue Scale [EQ VAS]).
- Duration of CR, defined as the time from first CR to time of relapse.

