### 7.3.3 Overall Survival

For the OS analysis, survival time is defined as the number of days from the day the subject was randomly assigned to study treatment to the date of death (regardless of cause).

$$\text{Survival time in days} = (\text{earliest date of death or censoring} - \text{date of randomization})$$

Survival time will be censored on the last date the subject is known alive with no event of death. OS curves will be estimated using Kaplan-Meier method and formally compared between the two treatment groups using a 2-sided stratified log-rank test, stratified by the same stratification factors used at randomization. The null and alternative hypotheses are:

- **Null hypothesis  $H_0$ :** Survival curves are the same between the two treatment arms
- **Alternative hypothesis  $H_1$ :** Survival curves are different between the two treatment arms

If the CR rate analysis is significant, OS will be tested at an alpha level of 0.05; without a significant CR rate test result, OS will be tested at an alpha level of 0.01, as described in Section 7.3.7. The stratification variables will include age (<75 or  $\geq$ 75 years), ECOG performance status (0-1, 2-3), study center region (North America, Europe, ROW), and secondary AML or poor-risk cytogenetics (Yes, No/Unknown). The median (and quartiles) duration of OS and the associated 95% CI for each treatment arm will be estimated using the Kaplan-Meier method and the  $\log(-\log(\cdot))$  transformation for the survival function. The 12-month survival rate estimate will also be provided for each treatment arm.

In addition, the HR and its 95% CI will be estimated using a Cox proportional-hazard model with treatment group as the independent variable and stratified by the same randomization stratification factors as used for the log-rank test. In a supportive analysis, the assumption of proportional hazards will be evaluated to assist interpretation of the Cox regression analysis results.

The following sensitivity analyses will be conducted for the co-primary endpoint of OS for evaluating robustness of the treatment effect:

- 1) The OS will be analyzed using Kaplan-Meier method and compared between the guadecitabine and TC using log-rank test without stratification.

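### The success rule on CR carries no OS condition, and no criterion is set for concluding from a non-significant OS result that survival is not reduced

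*SAP*

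**What the plan says.** Protocol 4.2 states why OS is there: "The trial includes a co-primary endpoint of OS to confirm no decrement in survival from severe toxicity". The SAP does not repeat this purpose.

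The success rule appears in the protocol synopsis, protocol 4.1 and 11.6, and SAP 7.3. Protocol 11.6 opens it with "If either of the co-primary efficacy endpoints reaches statistical significance in favor of SGI-110 at either the interim analysis (OS only) or final analysis". SAP 7.3 closes it with "then the study will be considered positive in efficacy". Significance must favour guadecitabine on the endpoint that wins. Nothing is required of the other endpoint.

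SAP 7.3.3 says that OS will be "formally compared between the two treatment groups using a 2-sided stratified log-rank test", with the alternative hypothesis "Survival curves are different between the two treatment arms". On the alpha level it says "If the CR rate analysis is significant, OS will be tested at an alpha level of 0.05"; otherwise the level is 0.01. The same section plans a stratified Cox HR with a 95% CI (protocol 11.6.3 allows 95% or 99%). SAP section 4.0 sizes OS for superiority: 670 deaths, 90% power, HR about 0.78.

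Neither document states a non-inferiority hypothesis, a margin, or a confidence limit that OS must meet.

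**The concern.** The protocol gives OS two roles. One is superiority, which has a test, an alpha level and an event count. The other is reassurance that survival is not reduced, which has no decision rule. A non-significant test of no difference does not show absence of harm, so if CR wins and OS does not, the plan does not say what may be concluded about survival.

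The success rule makes the gap matter. It is an either/or rule, and CR alone is enough. CR could win while toxicity costs lives, which is the risk that protocol 4.2 names, and the study would still carry the positive label. The risk is not remote from the sponsor's own data: Table 10 in protocol 2.1 shows grade 3 or higher febrile neutropenia in 51% on SGI-110, against 25% to 32% in the comparator arms with data. The same section calls early mortality comparable, so the documents do not predict harm.

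**Working it through.** **Inputs.** 670 deaths, 1:1 allocation, medians of 7 and 9 months (HR = 7/9 = 0.778), 400 subjects per arm, CR 0.20 against 0.30 at two-sided alpha 0.04 (all SAP 3.1 and 4.0). OS alpha is 0.05 after a CR win (SAP 7.3.3; 0.04995 after the interim, SAP 7.6).

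**1. The plan's own figures reproduce.**
- Deaths = 4(z₀.₉₇₅ + z₀.₉₀)² / (ln HR)² = 4(1.960 + 1.282)² / (0.2513)² ≈ 666. Power with 670 deaths is 0.902. With HR rounded to 0.78, the figures are 681 deaths and power 0.895. The stated 670 and 90% hold.
- CR power with 400 per arm is 0.889, against about 89% stated.

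**2. Precision of OS.** SE(ln HR) = 2/√670 = 0.0773. The 95% CI is the observed HR divided and multiplied by exp(1.96 × 0.0773) = 1.164.
- OS is significantly worse at two-sided 0.05 when the observed HR is about 1.164 or more.
- An observed HR of 1.00 gives a CI of 0.86 to 1.16. The upper limit corresponds to a median of 7/1.164 ≈ 6.0 months against 7 on TC, if survival is exponential.

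**3. How often the literal rule would give a positive label with OS significantly worse.** The documents give no adverse HR, so the true values below are assumptions. P(OS significantly worse) = Φ(ln HR/0.0773 − 1.96). The joint column multiplies this by CR power 0.889, assuming independence. The bounds hold for any correlation: from P + 0.889 − 1 up to the smaller of P and 0.889.

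| True OS HR | P(OS significantly worse) | Joint with CR win | Bounds |
|---|---|---|---|
| 1.00 | 2.5% | 2.2% | 0–2.5% |
| 1.10 | 23% | 21% | 12–23% |
| 1.20 | 66% | 58% | 54–66% |
| 1.25 | 82% | 73% | 71–82% |

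**4. What 670 deaths could support if a margin M were set.** The upper 95% limit lies below M when the observed HR is at most M/1.164. At true HR 1.00 the probability is Φ(ln M/0.0773 − 1.96).

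| Margin M (assumed) | Observed HR needed | Probability at true HR 1.00 | Deaths for 90% |
|---|---|---|---|
| 1.15 | ≤0.988 | 44% | 2152 |
| 1.20 | ≤1.031 | 66% | 1265 |
| 1.25 | ≤1.074 | 82% | 845 |
| 1.30 | ≤1.117 | 92% | 611 |

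At the design HR of 7/9 the probability exceeds 99% for each of these margins.

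**The case against.** The strongest reply is that the plan is not blind to survival harm, and this is right. The OS test is two-sided, so it tests for harm as well as benefit. The stratified HR with its 95% CI bounds any decrement. SAP 7.3.3 adds 12-month survival and four sensitivity analyses, and SAP 7.3.13 adds interval HRs if hazards are not proportional. Thirty- and 60-day mortality is summarised (SAP 7.4.3), and protocol 11.7 compares it by chi-square. The DMC reviews safety about every 6 months; its charter is not among the documents and may hold further rules. A reader might infer that OS is only a superiority test, or that no analysis could confirm that survival is preserved. The documents do not support either inference: a significant OS win would confirm it, with 90% power at an HR of about 0.78.

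A second reply is that the label covers efficacy only, not benefit-risk, and that an OS test that is not positive stops formal testing of CRc, NDAOH and PFS. That is also fair: harm would be visible, not hidden.

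A third is that the reassurance purpose rests on one sentence of design discussion, while the primary objective is simply to compare CR and OS. Rewording that sentence would remove the mismatch of purpose. It would leave the success rule unchanged.

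What remains is that none of these analyses feeds into the success rule, and none sets a criterion for a non-significant OS result.

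**Conclusion.** The point holds in a limited form. Protocol 4.2 assigns OS a purpose for which there is no pre-specified criterion when OS is not significant, and the CR success rule has no OS safeguard. Followed exactly, a CR win with an observed OS HR of about 1.164 or more would be labelled positive in efficacy. With an observed HR of 1.00, an HR of up to about 1.16 would remain unexcluded.

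These thresholds assume 670 deaths split about equally and the usual large-sample SE. The joint probabilities also assume CR is truly 0.30 against 0.20 and that the adverse HRs are as shown. The adverse HRs illustrate the rule and do not forecast harm. No figure stated in the plan is wrong.

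A reader might go further and ask for a fixed non-inferiority margin such as 1.25 as a condition of success. The documents give no basis for a particular margin, and 670 deaths would meet that one only 82% of the time at true HR 1.00. A binding margin is therefore a trade-off for the sponsor to justify, not a correction that follows from the plan.

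**What to change.** 1. In SAP 7.3, and in protocol 4.1, 11.6 and the synopsis, add that a win on CR alone is called positive only if the two-sided 95% CI of the stratified OS HR in the Efficacy Analysis Set does not lie wholly above 1.
2. In SAP 7.3.3, add that a non-significant OS test will not be reported as showing no reduction in survival. The conclusion will instead give the upper 95% limit of the HR as the largest decrement not excluded.
3. Reword the OS sentence in protocol 4.2 to match, unless the sponsor pre-specifies and justifies its own margin before database lock. In that case, state the probability of meeting it with 670 deaths.

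The cost is a few sentences, with no added subjects, events or data. Change 1 only adds a requirement to a positive call, so it cannot raise the type I error. If the true HR is 1, it withholds a CR-only win in at most about 2.5% of trials. Change 2 affects reporting only.
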